18	ATTACHMENTS	32

CONFIDENTIAL

List of Abbreviations

%AF	African Ancestry
AA	African American
AC	Attenuation Correction
ADC	Alzheimer's Disease Center
AE	Adverse Event/Adverse Experience
AD _{PiB} mask	AD-vulnerable ROIs PiB SUVR values
AD	Alzheimer's Disease
A β	Amyloid Beta
AHI4%	Apnea Hypopnea Index with 4% desaturation
BEDTIME	Brain Sleep Deprivation MRI Effects
BMI	Body Mass Index
CAB	Community Advisory Board
CBI	Center for Biomedical Imaging
CBO	Community Based
CSF	Cerebrospinal Fluid
CVD	Cardiovascular disease
CVE	Cardiovascular events
CRF	Case Report Form
CBH	Center for Brain Health
CDR	Clinical Dementia Rating
CHBC	Center for Healthful Behavior Change
CNS	Central Nervous System
CT	Completion Time
DKI	Diffusion Kurtosis Imaging
EKG	Electrocardiogram
FU	follow-up
FDA	Food and Drug Administration
FLAIR	Fluid-attenuated Inversion Recovery
HIPAA	Health Insurance Portability and Accountability Act
ICF	Informed Consent Form
ISF	Interstitial Fluid
IRB	Institutional Review Board
MoCA	Montreal Cognitive Assessment
MRI	Magnetic Resonance Imaging

CONFIDENTIAL

MCI	Mild Cognitive Impairment
mPFC	medial Prefrontal Cortex
n	Number
MSISC	Mount Sinai Integrative Sleep Center
NACC	National Alzheimer's Coordinating Center
NCRAD	National Cell Repository for Alzheimer's Disease
NIH	National Institutes of Health
NIA	National Institute on Aging
NREM	Non-REM
NYULMC	NYU Langone Medical Center
NPSG	Nocturnal Polysomnography
OSA	Obstructive Sleep Apnea
PS	Plasma Serum
PET	Positron Emission Tomography
PCP	Primary Care Physician
PI	Principal Investigator
PHI	Protected Health Information
PiB	Pittsburgh Compound B
RDI	Respiratory Disturbance Index
SNR	Signal to Noise Ratio
SAE	Serious Adverse Event/Serious Adverse Experience
SWA	Slow Wave Activity
SWS	Slow Wave Sleep
ROI	Region of Interest
SUVr	Standard Uptake Value Ratio
TST	Total Sleep Time
UTE	Ultrashort Echo Time
US	United States
UDS	Uniform Data Set
WASO	Wake After Sleep Onset
WHR	Waist to Hip Ratio
WML	White Matter Lesions

CONFIDENTIAL

Protocol Summary

Title	A SINGLE-CENTER, OBSERVATIONAL, LONGITUDINAL STUDY ON THE EFFECT OF SLOW WAVE SLEEP (SWS) CHARACTERISTICS, RACE AND ETHNICITY ON AMYLOID BURDEN (A MARKER OF ALZHEIMER'S DISEASE RISK), AMONG COGNITIVELY NORMAL ELDERLY
Short Title	The Sleep Amyloid, Slow WAve Race and Ethnicity (Sleep AWARE) study
Brief Summary	African-Americans (AAs) have an increased prevalence of both Alzheimer's disease (AD) and vascular risk factors for AD such as diabetes and hypertension when compared to whites. However, in a recent community based study of non-demented elderly, black race was associated with higher amyloid burden after adjusting for vascular risk factors, suggesting the presence of additional physiological differences on AD-risk by race in the early stages of the disease. The purpose of this study is to test whether poor slow wave sleep (SWS) quantity (SWS duration) and quality (slow wave activity, SWA) is one of these physiological factors. To test these hypotheses, we will perform community outreach in barbershops, churches and senior centers in Brooklyn and other NYC boroughs with which we have created substantial ties in recent years. In consultation with community stakeholders, we will recruit 150 cognitively normal AA elderly (age 60-75) and 60 age, sex, BMI, income and education matched non-Hispanic whites from the same geographical areas. We will first perform a medical and cognitive evaluation (Visit 1). Participants will then undergo 2 nights of home sleep monitoring using an unattended device to exclude OSA, followed by 7 days of actigraphy with a sleep log to record sleep duration. Both devices will be returned by mail. Subjects with reported total sleep time (TST) between 5 and 10 hours and absence of moderate to severe OSA will be invited to perform a 2-night nocturnal polysomnography (NPSG) (Nights 1-2) and a PiB-PET MR scan (Visit 2).
Objectives	Objective 1: To test if African ancestry (%AF) is associated with short SWS duration and poor SWA in older AAs. Objective 2: To test the effect of race and its interaction with baseline short SWS duration/poor SWA on longitudinal amyloid deposition. Objective 3: To test the effect of race and baseline poor SWA on cognition. Secondary Objective 2.1: To test whether loss of sleep-dependent spatial navigational memory at baseline is a predictor of cognitive decline.
Methodology	30-36 month longitudinal study
Endpoint	Primary endpoint is longitudinal increase in amyloid deposition
Study Duration	5 years
Participant Duration	30-36 months

CONFIDENTIAL

[figure not shown]
This material is the property of the NYU School of Medicine and Langone Medical Center. Do not disclose or use except as authorized in writing by the study sponsor


Population
	
210 cognitively normal elderly (Clinical Dementia Rating [CDR]=0), self-identified as African-American (AA) or non-Hispanic white (NHW), ages 60 to 75 years, with English as their primary language. The reason for only including native English speakers is due to the nature of the study and cognition being one of the outcomes of the study. The reason for including only African American blacks and NHW is the focus of this grant which is on African Americans and their African genetic ancestry and admixture. Based on our preliminary data an existing literature, in order for genetic admixture analyses to be applied rigorously, the control group needs to be of NHW. The definition of NHW are people in the United States who are considered racially white and are not of Hispanophone identity or the Hispanosphere (terms used to refer to Spanish-language speakers and the Spanish-speaking world as compared to for example English-speaking of French-speaking to name a few). Other non-English non-Hispanic white ethnicities will not be invited to participate due to the lack of adequate neuropsychological tools and testers proficient in other native European languages and the confounding effects of immigration. These NHW participants will be located within the same zip codes as the AAs.

Study Sites
	
NYU locations: the Center for Brain Health (CBH) at NYULMC, the Center for Biomedical Imaging (CBI), NYU Langone Health, Department of Radiology, [name]
 
External Site: the Mount Sinai Integrative Sleep Center (MSISC) (New York, NY)

Number of participants
	
210 participants expected to be enrolled with 150 cognitively normal African-American elderly and 60 non-Hispanic white.

Statistical Analysis
	
We will incorporate standard techniques such as omnibus tests and appropriate adjustments to significance (α) levels (e.g., Bonferroni correction) for post-hoc contrasts to control for multiple comparisons. Both selection and attrition biases might occur. Appropriate techniques (e.g., Heckman 2-stage approach (GEE Probit Model) and Monte Carlo (EM algorithm) will be used to address biases or missing data. Since only two time points will be analyzed, we will use linear regression models with the annual rate of amyloid change as dependent variable. Significance will be defined by $p < .05$ where p will be Bonferroni corrected when testing post-hoc contrasts.

CONFIDENTIAL

2.1 Background Information and Relevant Literature

Sleep duration in America has gradually declined over the last four decades, with current average sleep duration being of approximately 6 hours¹⁸. Parallel to this decline, African Americans (AAs) have the

CONFIDENTIAL

This material is the property of the NYU School of Medicine and Langone Medical Center. Do not disclose or use except as authorized in writing by the study sponsor

highest prevalence of long (≥ 9 h) and short sleep (≤ 6 h)⁶¹⁻⁶³, within the intervals commonly associated with morbidity and increased AD-risk⁶⁸⁻⁷⁰. AAs take longer to fall asleep¹⁸⁻²³, have lower sleep efficiency and have consistently shown to spend a smaller proportion of time in deep stages of non-REM (NREM) (also called slow wave sleep [SWS])^{19;20;23-28;32}. Possible mediators underlying these racial differences in sleep include age, sex, obesity, psychosocial factors, health care behaviors and medical disorders^{21;23;27;71-76}. A meta-analysis designed to estimate the magnitude of these variations in sleep, showed that racial/ethnic differences in sleep duration and continuity were moderated by the factors underlined above²³, while only psychosocial stressors (measured as perceived discrimination)^{20;21;26} were partially associated with the decreases in SWS duration, suggesting that race still remained an important independent risk factor for decreased SWS among AAs. A recent study confirmed this finding showing that decreased SWS duration was associated with an increased percentage of African ancestry (%AF)³⁹ even after adjusting for several demographic, socioeconomic and clinical covariates. Further replication is warranted, but African ancestry has also been associated to increased risk for hypertension⁷⁷ and diabetes⁷⁸ both of which have been linked with reductions in time spent in SWS^{79;80}.

Approximately 20% of healthy adults have mild and 6.6% moderate-to-severe obstructive sleep apnea (OSA)⁸¹, with a higher incidence occurring in the elderly⁸². AAs generally show a higher prevalence of OSA³³⁻³⁶. Specifically, in the Cleveland Family Study, AAs presented with OSA at a younger age³⁵, while Ancoli-Israel et al.³⁴ found that older AAs were 2.5 times more likely to have severe OSA. These findings are in agreement with another study of adults aged 40-60, where OSA rates were higher among minorities³³. In contrast, both the Sleep Heart Health (7% AAs) and Scharf's et al. studies failed to show higher rates of OSA in AAs after controlling for obesity^{83;84}. However, AAs from these studies suffered more excessive daytime sleepiness, in agreement to previous findings suggesting that OSA-associated symptoms might be more common in AAs^{34;85}. Apnea occurs less commonly during SWS, as SWS is associated with a higher respiratory arousal threshold^{86;87} and more stable breathing⁸⁸. However, beyond a certain threshold of frequency, apnea in any sleep stage impairs entry into SWS. In addition, the temporal course of slow wave activity (SWA) has shown to be slower in mild OSA⁸⁹, and severe OSA patients show up to a 40% rebound in SWS duration during treatment with CPAP⁹⁰. All the above findings suggest that changes in SWS are common in OSA patients. SWS disruption may therefore be another mechanism by which OSA increases AD risk⁹¹⁻⁹³.

In summary: certain ethnic groups are more likely to have disturbed sleep. AAs show clear independent differences in SWS characteristics but not in sleep duration or OSA prevalence when compared to whites, after controlling for socioeconomic factors, obesity or health care behaviors. These differences seem unrelated to other explanatory factors (except for the partial effect of psychosocial stressors) and suggest that AAs may have less restorative sleep than whites. The brain consequences of these decreases in SWS are not known.

2.2 Rationale

Primary Aims. To examine: *i*) whether African Ancestry (%AF) is associated with decreased SWS duration and SWA; *ii*) the effects of race on longitudinal amyloid build-up and its interaction with baseline SWS duration and SWA in cognitively normal elderly; *iii*) the effects of race and its interaction with baseline SWA on longitudinal changes in global cognition, memory, executive function and a spatial navigational memory task. **Exploratory aim.** We will test whether loss of sleep-dependent spatial navigational memory at baseline is a predictor of cognitive decline at follow-up.

Rationale for ethnicity/nativity and clinical groups selection:

Multiethnic cohort studies provide better information about disease causation but they are expensive to design. We will focus on 150 African-American (AA) blacks since African or Caribbean-born are not equally admixed and inclusion of more ethnic groups would result in loss of power for Aim 1 and need for great increases in sample size. As a comparison group, we will include 60 matched non-Hispanic whites. Race will be represented both as binary (self-identified AA vs. self-identified white) and numeric (% of African ancestry). Irregular sleep-wake rhythms and extreme sleep durations may also increase AD risk⁶⁸⁻⁷⁰. The study will not formally test these sleep disorders, as these subjects are hard to recruit in community-based

CONFIDENTIAL

studies (often reluctant to participate in studies that monitor sleep) and the focus is on SWS. Insomnia will be allowed as long as total sleep time (TST) is between 5-9 hours based on actigraphy recordings and sleep logs performed at home.

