3.1 Primary Objective

Aim 1 will test if African ancestry (%AF) is associated with short SWS duration and poor SWA in older AAs. **Challenge:** AAs consistently spend less time in SWS than whites²³⁻³². Although SWS shows significant heritability, social stressors may moderate these differences. **Approach:** test whether %AF⁴⁰ is associated with SWS characteristics after controlling for psychosocial factors (*e.g.* stress related to ethnicity). **Outcome:** positive results would suggest that racial differences in SWS have genetic underpinnings.

Aim 2 will test the effect of race and its interaction with baseline short SWS duration/poor SWA on longitudinal amyloid deposition. **Challenge:** AAs spend less time in SWS²³⁻³², a sleep stage important for A β dynamics⁴¹⁻⁴³ that may confer protection against amyloid deposition⁴⁴. **Approach:** assess how race is associated with longitudinal PiB uptake and its interaction with short SWS duration and poor SWA, after controlling for: 1) medial prefrontal (mPFC) atrophy, TST, AHI4% and cerebrovascular damage (measured as white matter lesion [WML] volume and abnormal diffusion kurtosis imaging [DKI] indices); and, 2) psychosocial factors, health care behaviors and medical morbidity. **Outcome:** reduced SWS/SWA would become a novel risk factor for AD in African Americans (AAs).

Aim 3 will test the effect of race and baseline poor SWA on cognition. **Challenge:** race and poor sleep have been associated with cognitive impairment. However, most studies are confounded by the inclusion of OSA patients, subjective measurements of sleep, lack of valid cognitive assessments for AAs and inadequate enrollment of minorities. **Approach:** we will test for the association between race and longitudinal changes in global cognition, memory, executive function and a sleep-dependent spatial navigational memory task. In addition, we will test their interaction with baseline SWA, using a similar approach as in Aim 2. **Outcome:** positive results would emphasize the importance of health messages promoting good sleep hygiene among AA elderly.

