9.3 Statistical Methods

General considerations: we will incorporate standard techniques such as omnibus tests and appropriate adjustments to significance (α) levels (*e.g.*, Bonferroni correction) for *post-hoc* contrasts to control for multiple comparisons. Both selection and attrition biases might occur. Appropriate techniques (*e.g.*, Heckman 2-stage approach (GEE Probit Model)^{254;255} and Monte Carlo (EM algorithm)²⁵⁶ will be used to address biases or missing data. Attributes of those who withdrew to follow-up will be contrasted with completers to determine sources of attrition biases. Since only two time points will be analyzed, we will use linear regression models with the annual rate of amyloid change as dependent variable. Significance will be defined by $p < .05$ where p will be Bonferroni corrected when testing *post-hoc* contrasts.

- **Hypothesis (1)**: H1.1) for %AF associations, linear regression models, with each of SWS characteristics as the dependent variable, will be regressed on %AF controlling for age, sex, BMI, AHI, TST, sleep efficiency and WASO. H1.2) This model will test interaction by including the best SWS predictor as dependent variable, the psychosocial factor as a classification factor, %AF and the term created as the cross product of psychosocial factors and %AF.
- **Hypothesis 2-3 (H2-3)**: First we will calculate the associations between race and AD_{PiB}mask represented both as binary (AA *vs.* white) and numeric (%AF). Further analyses will use the representation (s) of race significantly associated with amyloid burden. Second, we will use hierarchical

CONFIDENTIAL

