linear regression, with rate of change of AD_{PiB}mask as the dependent variable and race as independent, adjusting for the matching factors: age, sex, BMI, education and annual income (block 1); ApoE4 and ABCA7 (block 2); DWML volumes, DKI indices and mPFC volume (block 3); and SWS characteristic (*e.g.* relative SWA) (block 4). Other covariates (*e.g.*, psychosocial) will be included in the final models if significantly different between AAs and whites as indicated by unequal variance t tests. Although we anticipate that relative SWA will be the best predictor of longitudinal change in AD_{PiB}mask, the best fitting model will be then replicated with each of the other SWS characteristics not listed before. On a final step, we will test whether the effect of SWS on amyloid deposition is different (*i.e.*, stronger) among AAs. The model would include AD_{PiB}mask change, the binary indicator of race (AA=1 *vs.* white=0) and SWA as described in H1.2. If the interaction is significant, it will imply that the effect of SWA on amyloid varies as a function of race. The sign of the estimated coefficient for this term would indicate whether SWA has a significantly stronger or weaker effect among AA. Exploratory Hypothesis: cognitive z-score change in subjects that show improvement in maze CT will be compared with those that don't show improvement using ANCOVA controlling for age, sex, BMI, race, education and ApoE4 status.

- **Post-hoc analyses**: a subset of *post-hoc* analyses will be performed by controlling by PiB levels at baseline and by splitting the sample into PiB+ and PiB- at baseline and performing a separate analysis for each subset. Stratified analyses will also be performed for men and women, as well as for AAs and whites. In addition, we will formally test the impact of PiB status (defined as PiB SUVR \geq 1.4) on the association of sleep measures with longitudinal increases in AD_{PiB}mask. Although we do not anticipate that sleep or SWS characteristics will change over the follow-up period, *post-hoc* analyses will be performed by assessing longitudinal changes in the sleep measures as correlates and predictors of longitudinal changes in the outcomes measures, using paired sample t-tests to assess the change in outcomes and sleep.

10 Source Documents and Access to Source Data/Documents

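### In H2-3, %AF is an alternative coding of race with no AA-only limit; fitted across both groups it would mainly restate the AA-white difference and could not by itself support an ancestry effect

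*Combined protocol and SAP*

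**What the plan says.** Section 2.2 (Rationale) sets up two codings: "Race will be represented both as binary (self-identified AA vs. self-identified white) and numeric (% of African ancestry". Section 9.3, Hypothesis 2-3, uses both in one step, "First we will calculate the associations between race and AD_{PiB}mask represented both as binary (AA *vs.* white) and numeric (%AF", and then lets the result decide: "Further analyses will use the representation (s) of race significantly associated with amyloid burden".

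The hierarchical model that follows has race as the independent variable, "adjusting for the matching factors: age, sex, BMI, education and annual income (block 1); ApoE4 and ABCA7 (block 2", then imaging measures (block 3) and a slow wave sleep (SWS) characteristic (block 4). Self-identified race is not listed as a covariate for the case where %AF is the chosen coding. The last step, the test of whether the sleep effect differs by race, uses the indicator only: "The model would include AD_{PiB}mask change, the binary indicator of race (AA=1 *vs.* white=0) and SWA as described in H1.2". Among the post-hoc analyses, "Stratified analyses will also be performed for men and women, as well as for AAs and whites".

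Two other places bear on how %AF will be read. The Protocol Summary (Population) says that "in order for genetic admixture analyses to be applied rigorously, the control group needs to be of NHW". Section 3.1 words Aim 1 as a question within older AAs and says that "positive results would suggest that racial differences in SWS have genetic underpinnings".

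**The concern.** The AA/white indicator needs both groups. %AF is offered as its alternative in the same step, with no limit to AAs, so the natural reading is that %AF is also fitted across both groups. There it has two clusters, one near zero and one high, and its slope is driven mainly by the distance between them. Only the variation in %AF among AAs can separate ancestry from self-identified race.

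What is at stake is interpretation. If %AF is the coding carried forward, its coefficient looks like a gradient in genetic ancestry but would be much the same number as the race contrast. If it is only a second coding of race, it adds little information and gives a second chance at p<.05.

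**Working it through.** **1. The plan's own %AF figure.** Section 9.2 gives 80% power at the 5% level for |r|=0.20 (Aim 1). By Fisher's z, two-sided, n = ((1.960 + 0.842)/atanh(0.20))² + 3 = 194, and N=200 gives 81.2% power. The figure is reproduced for about 200 subjects. With 150 AAs alone, power at 0.20 is 69.1% two-sided or 79.2% one-sided; the plan does not state sidedness. No power figure is given for %AF in Aims 2-3.

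**2. Correlation of pooled %AF with binary race.** Group sizes are 150 and 60 (Protocol Summary), so p = 150/210 = 0.714. The %AF means and SDs are assumptions. With mean difference d and within-group variance W = p·SD²(AA) + (1−p)·SD²(white),

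r² = d²p(1−p) / (d²p(1−p) + W).

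Example, AA 80/10 and white 1/2: d²p(1−p) = 79² × 0.2041 = 1273.7; W = 71.4 + 1.1 = 72.6; r² = 0.946; r = 0.973.

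Before covariates, r² is also the weight that the pooled least-squares slope gives to the between-group gap, and 1−r² is the weight left for variation within groups.

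**3. What a pure race gap does to the pooled %AF test.** Take a gap that gives the indicator 80% power at N=200 (correlation 0.197), with no ancestry slope inside either group. The correlation of pooled %AF with the outcome is then 0.197·r, and its power is Φ(atanh(0.197·r)·√197 − 1.960). The simulation used 143 AAs and 57 whites (200 × 150/210 = 143), a gap of 0.44 SD and 5,000 runs.

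| AA mean/SD; white mean/SD (assumed) | r | r² | 1−r² | Pooled %AF significant, formula | Simulated |
|---|---|---|---|---|---|
| 85/8; 1/1 | 0.984 | 0.969 | 0.031 | 78.7% | not run |
| 80/10; 1/2 | 0.973 | 0.946 | 0.054 | 77.7% | 78.2% |
| 80/15; 2/3 | 0.940 | 0.884 | 0.116 | 74.8% | not run |
| 75/15; 3/5 | 0.929 | 0.863 | 0.137 | 73.8% | 74.6% |
| 70/20; 5/5 | 0.864 | 0.746 | 0.254 | 67.5% | 67.3% |
| 60/25; 5/5 (extreme) | 0.759 | 0.576 | 0.424 | 56.2% | not run |

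A second simulation (4,000 trials per setting, whites near 0 to 1, gap 0.445 SD) gave 80% at AA 85/8 (r=0.985), 79% at 80/10, 76% at 75/15 and 72% at 70/18 (r=0.906). Across both sets, %AF tested inside AAs only was significant in 4.4% to 5.4% of runs. In the first set, pooled %AF adjusted for the indicator was significant in 4.5% to 5.3%.

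**4. Choosing the coding by significance.** With no race effect at all, and two test statistics correlated at r, the chance that at least one coding reaches p<.05 is 5.8% at r=0.984 and 7.4% at r=0.864.

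**5. Precision of a within-AA term.** With 143 AAs, the detectable |r| at 80% power is tanh(2.802/√140) = 0.232. Power at |r|=0.20 is Φ(0.2027 × 11.83 − 1.960) = 67%.

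**The case against.** The strongest reply is that Aims 2-3 make no genetic claim. Hypotheses 2.1 to 3.2 speak of race, and section 2.2 calls %AF a representation of race, so a %AF slope that tracks the race contrast does what it is meant to do. A reader might infer that the protocol plans to report a pooled slope as a genetic effect on amyloid. The documents do not support that: the statement about genetic underpinnings belongs to Aim 1, concerns SWS, and is worded for AAs. Nor are the 67% to 80% figures false-positive rates for the plan's race hypothesis. They are error rates only for an ancestry reading.

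A reader might also infer that pooling is stated. It is not. Section 9.3 is equally silent about the population for H1.1, where section 3.1 supplies the limit to AAs, so silence there is weak evidence. Pooling remains the natural reading because %AF is offered as an alternative to a coding that needs both groups.

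A third tempting reading is that the slope would carry every social and clinical difference between the groups. That is too strong. Section 4 balances the groups on sex, age, BMI, income and education within the same zip codes. Blocks 1 to 3 adjust for these matching factors, for ApoE4 and ABCA7, and for imaging measures, and psychosocial covariates enter if they differ between groups. This reduces the group difference but does not separate %AF from self-identified race.

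The stratified AA/white analysis could expose the problem, but it is post hoc and not tied to %AF. The final interaction step uses the indicator only and is not affected. Finally, the near-identity of the two codings weakens if admixture among AAs is wide: within-group variation then gets about 25% of the weight at r=0.864 and 42% at r=0.759.

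**Conclusion.** The concern holds as a gap in specification and interpretation. On the natural reading, %AF in H2-3 would correlate about 0.86 to 0.985 with the AA/white indicator. Its slope would mainly restate the adjusted AA-white difference and could not by itself support an ancestry effect on amyloid or cognition. The size rests on assumed AA %AF means of 70 to 85 and SDs of 8 to 20, with whites near zero (means up to 5), and on calculations without covariates. Selection by significance adds a smaller problem, a null rejection rate of about 5.8% to 7.4% instead of 5%. If a within-AA fit was intended, the calculation does not apply, but section 9.3 still has to say so. The point merits a change before analysis; it does not put the binary race contrast or the interaction test in doubt.

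**What to change.** In section 9.3, Hypothesis 2-3, enter the AA/white indicator together with %AF centered at the AA mean within AAs and set to 0 in whites. The centered values sum to zero among AAs, so before covariates the two terms are uncorrelated. Interpret the first coefficient as the race contrast and only the second as evidence on ancestry. Delete the rule that selects the representation of race by significance.

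This takes about one sentence and no new data. The cost is that the ancestry term draws only on the AAs, about 143 of 200 completers: it detects |r| of about 0.23 at 80% power and has about 67% power at |r|=0.20. H2-3 state no within-AA ancestry hypothesis, so the plan should also say what role this second term has.
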